Title: Do Peanut-Shaped Birthing Balls Reduce the Length of Labor in Patients with Epidural Analgesia?

Primary Investigator: [name]

Background:

In the United States approximately 2/3 of laboring women receive epidural or combined spinal-epidural (CSE) analgesia.1 A 1998 meta-analysis found that although epidural analgesia increases the length of labor by 56 min, it does not increase the incidence of cesarean delivery or forceps delivery for dystocia.2 Additionally, maternal satisfaction is significantly increased in patients with epidural analgesia. For a number of reasons unrelated to epidural analgesia, the incidence of cesarean delivery has increased during the past 20 years, and in 2013, 32.7% of women in the United States had a cesarean delivery.3 Because more than 90% of women that have a cesarean delivery have a repeat cesarean for subsequent deliveries and cesarean delivery is associated with more serious complications than vaginal delivery, there are national initiatives to reduce cesarean delivery rates.4 In a recently published study conducted by nurses and doulas in an Arizona hospital, the use of peanut-shaped birthing balls₅ (see Appendix, figure 1) in patients with epidural labor analgesia significantly reduced the length of labor and the incidence of cesarean delivery. Following epidural insertion and informed consent, patients were randomized to labor using a peanut ball or labor without using a peanut ball until complete cervical dilatation. The length of labor was reduced by 113 min (Stage 1 labor by 90min and Stage 2 labor by 23min) and the incidence of cesarean delivery was reduced by 57% (from 23.7 to 10.3%). No patient in either group experience complications. It is theorized that the birthing balls enhance labor by increasing the pelvic diameter, thus allowing for more rapid descent of the fetal head.

These results are incredibly significant for a single simple intervention and, if replicated, may have large scale public health implications. The purpose of the current study is to determine if a low-cost, safe, and easy to use physical prop actually improves labor outcomes. Thus, the hypothesis of this randomized prospective study is that use of peanut-shaped birthing balls following epidural administration will significantly reduce the length of labor and the incidence of operative delivery.

Method: After informed consent, up to 240 nulliparous parturients planning to request epidural analgesia for their labor pain will be enrolled in the study. Following CSE analgesia (patients will be standardized to the CSE technique because it has been suggested that CSE analgesia speeds the rate of cervical dilatation when compared to epidural analgesia⁷), patients will be randomized to either have a 45cm peanut-shaped birthing ball placed between the knees for the duration of stage 1 labor (until complete cervical dilation) or to labor as is customary without an object placed between the knees. To determine the impact of the birthing balls on the labor curve, patients will have a cervical exam within 15min of epidural placement and every four hours (or when clinically indicated) until complete cervical dilation. In addition, all patients will have a Bishop's score (used to assess the odds of successful vaginal birth) estimated by the obstetric team.⁸ Patients will be positioned

during labor in the lateral or semi-Fowler positions (see Appendix, figure 2) and asked to turn sides every hour. The length of labor from epidural insertion to delivery (the primary outcome) and the mode of delivery (secondary outcome) as well as usual variables such as the frequency and incidence of needing epidural top-ups, pain intensity, vital signs, fetal heart rate tracing, and patient satisfaction will be obtained throughout the course of labor and delivery. Following delivery, neonatal weight and Apgar scores will be recorded and all patients will be evaluated the day after delivery for satisfaction and any complications such as back or hip discomfort. Exclusion criteria: age<18, non-English speaking, multiparous women, patients with preeclampsia with documented abnormal liver enzyme function changes, contraindications to receiving neuraxial analgesia or any drugs used in this study.

Statistics and Analysis:

The primary outcome is the length of labor from epidural catheter insertion until delivery. Secondary outcomes include mode of delivery, maternal satisfaction and post-delivery complications. A power analysis was determined using historical data from epidural analgesia studies at FMC, recent FMC length of labor statistics, and estimations on length of labor reductions from the Banner Health report. To detect a 13% change in length of labor between groups with an estimated standard deviation of 46% from average length of labor (historical FMC mean =/- SD from epidural insertion to delivery is 325+/-150min), a minimum sample size of 101 per group is needed to provide a power of 0.8 and alpha of 0.05. We will enroll up to a total of 240 subjects (120 per group for 2 groups) in anticipation of potential exclusions. The study will conclude when 202 evaluable patients have completed the study.

Implications:

If peanut-shaped birthing balls improve labor outcomes without complications, practice protocols will be revised to include the routine use of them during labor in the Women's Center and possibly throughout all Novant birthing facilities. Further, publication of the results from this study will potentially affect public health policies.

Risks:

Epidural and CSE analgesia are commonly used (85%) in laboring patients at FMC (approximately 50-50 ratio). All of the usual risks for CSE labor analgesia apply including: inadequate anesthesia/analgesia, post dural puncture headache, backache, pruritus, nausea/vomiting, hypotension, as well as other very rare risks of respiratory depression, nerve injury, hematoma, infection and seizures. Although the Banner Health reports suggests that no patient experienced complications, we theorize that there is a small risk that use of the peanut-shaped birthing balls may increase the incidence of hip, pelvis or back discomfort following delivery. Patients will receive informed consent and will be treated as usual for any complications throughout labor and following delivery. All patients will be administered routine CSE medications throughout labor.

Benefits:

The results of this study may provide us a better understanding of the role of pelvic widening on labor outcomes.

Human Subjects Protection:

Written informed consent will be obtained from each subject. Study team members or the research nurse will obtain informed consent from patients in labor and delivery suite after determining their fulfillment for eligibility criteria in participation. The study and informed consent will be reviewed with the patients while they are in the labor and delivery suite. Once signed, a copy of the informed consent form will be placed in the patient's medical record and a copy will be given to the patient for their records.

Confidentiality will be protected by collecting only information needed to assess study outcomes, minimizing to the fullest extent possible the collection of any information that could directly identify subjects, and maintaining all study information in a secure manner. The master study enrollment log containing the names, group allocation, and date of study will be kept secure in the department of OB Anesthesia, with access limited to designated study personnel. Following data collection subject identifying information will be destroyed at the earliest opportunity, consistent with data validation and study design, producing an anonymous analytical data set. Data access will be limited to study staff. Data and records will be kept locked and secured, with any computer data password protected. No reference to any identifiable individual participant will appear in reports, presentations, or publications that may arise from the study.

Data and Safety Monitoring:

The principal investigator will be responsible for the overall monitoring of the data and safety of study participants. The principal investigator will be assisted by other members of the study staff. A data safety monitoring committee made up of 1 obstetrician and 1 obstetric anesthesiologist will be utilized and un-blinded to group allocation. They will review the interim results including review of vital signs, analgesic effects and the occurrence of any adverse events/side effects.

Reporting of Unanticipated Problems or Serious Adverse Events:

Any unanticipated problems, serious and unexpected adverse events protocol changes will be promptly reported by the principal investigator or designated member of the research team to the Institutional Review Board (IRB).

References:

1. Bucklin BA, et al. Obstetric anesthesia workforce survey: twenty-year update. Anesthesiology 2005; 103: 645-53.

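### Does the lack of a stage-of-labor entry criterion spoil the comparison, since a completely dilated patient could be randomized with no time to use the ball?

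*Combined protocol and SAP*

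**What the plan says.** The Method section of the combined protocol and SAP enrolls "nulliparous parturients planning to request epidural analgesia for their labor pain will be enrolled in the study". Patients are randomized after CSE. Those in the ball arm have it "placed between the knees for the duration of stage 1 labor (until complete cervical dilation".

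The exclusions cover age, language, parity, one form of preeclampsia, and contraindications to neuraxial analgesia or the study drugs: "Exclusion criteria: age<18, non-English speaking, multiparous women, patients with preeclampsia with documented abnormal liver enzyme function changes, contraindications to receiving neuraxial analgesia". None concerns dilation or stage of labor.

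The same section schedules an examination close to allocation: "patients will have a cervical exam within 15min of epidural placement and every four hours (or when clinically indicated) until complete cervical dilation". Its stated purpose is to describe the labor curve. The text does not say whether it comes before or after randomization, or that its result can stop allocation.

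Under Human Subjects Protection, consent is obtained "after determining their fulfillment for eligibility criteria in participation", so eligibility is settled before consent. No second check at randomization is described.

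Statistics and Analysis defines the primary outcome as time from catheter insertion to delivery, and adds: "The study will conclude when 202 evaluable patients have completed the study". It does not define evaluable.

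**The concern.** The intervention ends at complete dilation, whereas the outcome clock runs from catheter insertion to delivery. Labor can progress between the eligibility check and allocation. A patient who is completely dilated once the CSE is in place meets every listed criterion, contributes to the primary outcome, and cannot receive the assigned treatment in either arm.

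Two consequences suggest themselves:

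- **Dilution.** Patients with no possible effect pull the between-group difference toward zero and cost power.
- **One-sided exclusion.** Not using the ball is visible only in the ball arm. If evaluable were taken to mean that the ball was used, short times would be removed from that arm while their control counterparts stayed, and the result would be biased against the ball.

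**Working it through.** **Inputs from Statistics and Analysis:** historical mean 325 min, SD 150 min (46% of the mean); target 13%, or 0.13 × 325 = 42.25 min; power 0.80; alpha 0.05; 101 per group, 202 in total.

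**Assumed, because the documents give no figure:** share f of patients completely dilated at randomization, 2% or 5% (0.02 × 202 ≈ 4; 0.05 × 202 ≈ 10); their mean time to delivery m, 120 min (range 60 to 180).

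**The plan's own figure.** A two-sided two-sample t-test with d = 0.13/0.46 = 0.2826 needs 198 per group for 80% power, so 101 is not reproduced. That is a separate matter. To isolate the present point, dilution is shown first for a design that truly has 80% power.

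**Dilution.** If a share f has no effect and the SD is unchanged, the difference becomes (1 − f) × 42.25 and the required sample size grows by 1/(1 − f)².

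| f | difference (min) | power at 198 per group | sample size factor |
|---|---|---|---|
| 0 | 42.25 | 0.801 | 1.00 |
| 2% | 41.4 | 0.785 | 1.04 |
| 5% | 40.1 | 0.760 | 1.11 |

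At the planned 101 per group, power for the same differences is about 0.52, 0.50 and 0.48. The drop is small beside the shortfall already there.

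**Does the dilution apply at all?** Only if 42.25 min is the effect in patients who still have stage 1 ahead of them. The plan states the target as a change between groups and scales it to the hospital's insertion-to-delivery mean, with no restriction by dilation. A difference between groups averages over all who are randomized. On that reading any such patients are already in the target, and the further power loss is zero.

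**One-sided exclusion, had it happened.** Dropping a share f with mean m from the ball arm only, with arm mean 325 (no treatment effect), shifts that mean by f × (325 − m)/(1 − f):

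- f = 2%: 0.02 × 205/0.98 = 4.2 min (3.0 at m = 180; 5.4 at m = 60)
- f = 5%: 0.05 × 205/0.95 = 10.8 min (7.6 at m = 180; 13.9 at m = 60)

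The standard error of the difference at 101 per group is 150 × √(2/101) = 21.1 min. The central shifts are therefore 4.2/21.1 = 0.2 and 10.8/21.1 = 0.5 standard errors.

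**What that bias would require.** A completely dilated patient is randomized; evaluable is read as having used the ball; and the reading is applied in one arm. None of these is written in the plan. The examination soon after epidural placement is scheduled for patients in both arms alike, so any exclusion based on its result could be applied equally.

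**The case for a change.** The strongest case for a change is that it would cost almost nothing: one eligibility line and a fixed order for an examination already scheduled. The wording about stage 1 describes how long the ball is used and is not a condition of entry. The examination serves the labor curve. The plan enrolls 120 per group to obtain 101, an allowance of 19 per arm that reads most naturally as losses after allocation, and nowhere does it say that all randomized patients are analyzed in their allocated group. At 5%, a one-sided exclusion would shift the ball-arm mean by 7.6/42.25 = 18% to 13.9/42.25 = 33% of the target.

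The description of the text stands: the criterion is absent, and nothing forbids selective dropping. The conclusion does not follow from it. The bias comes from the undefined analysis population, which would matter equally for a patient who declines the ball or removes it early. An entry criterion would not cure that, and defining the population would cure it without one. What remains for the entry criterion is the dilution. There it helps only partly, because patients close to complete dilation would still be randomized and use the ball briefly. It would also narrow the population, whereas the Background's hypothesis concerns use after an epidural in general and the Implications section looks to routine use in labor. Randomizing all eligible nulliparas after CSE is a fair pragmatic choice.

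**Conclusion.** The omission is genuine but minor, and no change to the plan is called for. Analyzed as randomized, completely dilated patients do not bias the comparison. The loss of power is nil if the 13% target averages over everyone randomized, which is the plain reading. Otherwise it is about 2 points at an assumed 2% and 4 points at an assumed 5%. The documents support neither share; with a historical mean of 325 min from insertion to delivery in this nulliparous trial's planning, the true share is probably small. A regimen written for stage 1 presupposes stage 1, and staff can be expected to fill the gap sensibly. Stating the criterion would be a harmless clarification with little to gain.

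This rests on analysis by allocated group. The plan's failure to define evaluable, or to name its analysis population, is a separate point and should be judged on its own.

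### No primary model is named, and cervical dilation near the start of the outcome clock is collected but neither prespecified as a covariate nor required to be recorded before allocation

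*Combined protocol and SAP*

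**What the plan says.** The Statistics and Analysis section defines the endpoint: "The primary outcome is the length of labor from epidural catheter insertion until delivery". It then lists secondary outcomes, power inputs and enrollment targets. It names no test, model, covariate or stratification factor for the primary comparison, and none appears elsewhere. The sample size uses the unadjusted spread: "historical FMC mean =/- SD from epidural insertion to delivery is 325+/-150min".

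The Method section plans two measurements that bear on how far labor has progressed:

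- A cervical exam near time zero: "patients will have a cervical exam within 15min of epidural placement and every four hours (or when clinically indicated) until complete cervical dilation". Its stated purpose is "To determine the impact of the birthing balls on the labor curve"; use as a baseline covariate is not mentioned.
- A Bishop's score: "all patients will have a Bishop's score (used to assess the odds of successful vaginal birth) estimated by the obstetric team". No collection time and no role in the analysis are given.

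Randomization comes after CSE analgesia, when "patients will be randomized to either have a 45cm peanut-shaped birthing ball placed between the knees" or to labor without one. The text does not say whether the first exam comes before or after that step. The exclusion list ("Exclusion criteria: age<18, non-English speaking, multiparous women, patients with preeclampsia with documented abnormal liver enzyme function changes", followed by contraindications to neuraxial analgesia or study drugs) contains no dilation criterion.

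**The concern.** The outcome is the time remaining to delivery, and it includes the time still needed to reach complete dilation. Dilation when the clock starts says how much of that path has already been covered, so it should be prognostic. With no dilation criterion for entry, it can vary between patients, and in an unadjusted analysis the variation it explains stays in the error term.

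Three things are at stake:

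- **Precision.** A value the trial already collects could reduce the residual variance at no extra burden.
- **Prespecification.** With no model named, the choice between adjusted and unadjusted results can be made after the data are seen. The Implications section says a favorable result will change practice protocols, so this freedom matters.
- **A clean baseline.** The ball is visible. An exam read after allocation could be influenced by knowledge of the arm and would not strictly be a pre-randomization value. This cannot be repaired once patients have been enrolled.

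Randomization protects the unadjusted comparison, so bias in that comparison is not the issue.

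**Working it through.** **Inputs from Statistics and Analysis.** Mean 325 min, SD 150 min (46% of the mean), change of 13% (0.13 × 325 = 42.25 min), alpha 0.05, power 0.8, 101 per group, ceiling of 120 per group. Sidedness is not stated; two-sided is assumed.

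**Assumed input.** R-squared of dilation with epidural-to-delivery time. The documents give none. The range shown is 0.1 to 0.3, with 0.04 (a correlation of 0.2) as a low case.

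**The plan's own figure.** The standardized effect is d = 0.13/0.46 = 0.2826 (0.2817 from 42.25/150). A two-sided, two-group t test needs 198 per group (199 with d = 0.2817), so the stated 101 does not reproduce. A one-sample or paired t calculation with d = 0.2817 gives 100.87, that is 101, but this is a parallel two-group trial. That error is a separate point. Here it only sets the unadjusted starting value.

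**Effect of adjustment.** The residual SD is 150 × √(1 − R²), and the effective effect size is d/√(1 − R²). Power comes from the noncentral t, with one degree of freedom lost for the covariate. The required number scales by about (1 − R²): 198 × 0.9 = 178.2, 198 × 0.8 = 158.4, 198 × 0.7 = 138.6. The exact results, with d = 0.2826, are:

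| R² | Residual SD (min) | Power, 101/group | Power, 120/group | n/group for 80% | Detectable difference at 101/group, 80% power (min) |
|---|---|---|---|---|---|
| 0 | 150 | 52% | 59% | 198 | 59 |
| 0.04 | 147.0 | 53% | 60% | 190 | 58 |
| 0.1 | 142.3 | 56% | 63% | 178 | 56 |
| 0.2 | 134.2 | 61% | 68% | 159 | 53 |
| 0.3 | 125.5 | 67% | 74% | 139 | 50 |

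The detectable difference is computed with the SD of 150 min. With d = 0.2817, the power figures fall by about 0.3 percentage points and the required numbers rise by one or two per group.

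**R-squared at which adjustment alone gives 80% power.** It is 0.491 at 101 per group (0.494 with d = 0.2817) and 0.394 at 120 per group. By the normal approximation, the unadjusted requirement is 2 × 98.93 = 197.9 per group, and 1 − 101/197.9 = 0.49, a correlation of about 0.70.

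**Simulation.** In 20,000 trials with normal errors, 101 per group and an effect of 42.25 min, adjusted power was 0.554, 0.601 and 0.660 at R² of 0.1, 0.2 and 0.3, and 0.794 at 0.49. Unadjusted power was 0.507 to 0.516. Type I error was 0.050 unadjusted and 0.050 to 0.052 adjusted. This confirms the formula under normal errors; it does not model cesarean delivery.

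**The case against.** The strongest reply is that an unadjusted two-group comparison is legitimate, and that naming any primary analysis in advance, even an unadjusted one, would remove the scope for a post hoc choice. That is correct: prespecification alone does not require this covariate. The case for the covariate rests on precision.

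Second, the size of the gain has no source in the documents. The one prognostic remark concerns the Bishop's score and vaginal birth, which is mode of delivery and not duration. At an R-squared of 0.04 the gain at 101 per group is under two percentage points. This stands, and the low case is in the table. It shrinks the gain without reversing it.

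Third, the 150 min SD is historical, with parity and technique not stated, whereas this trial restricts entry to nulliparas and standardizes to CSE. The actual SD may differ. Sizing on the unadjusted SD is also the cautious choice when the correlation is unknown, so it is not itself a fault.

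Fourth, the 52% starting power comes from the sample-size error. Only the increment, about 4 to 15 points over R-squared 0.1 to 0.3, belongs here.

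Fifth, cesarean delivery also ends the clock and could change how early dilation relates to recorded time. The gain is therefore uncertain until cesarean handling is settled.

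Finally, nothing says the exam follows allocation, and any ball use before it would last minutes at most. Contamination is a possibility, not a demonstrated fault. It matters only if dilation is used as a covariate, and then an ordering rule removes it.

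**Conclusion.** The concern holds, as a low-cost improvement that should be made. The text establishes that no primary model or covariate is named, that dilation is measured close to time zero, and that its order relative to allocation is not fixed. That dilation is prognostic is an inference from the outcome's definition. Its strength is unknown, so confidence in the size of the benefit is medium.

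If R-squared lies between 0.1 and 0.3, adjustment at the planned 101 per group cuts the detectable difference by about 3 to 10 min (59.4 − 56.4 = 3.0; 59.4 − 49.7 = 9.7). These figures assume a two-sided test, the historical SD and a linear relation. In that range adjustment does not bring the trial to 80% power, even at 120 per group.

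**What to change.** In Statistics and Analysis, name the primary analysis: a linear model of epidural-to-delivery time with arm and cervical dilation at epidural placement, and the unadjusted comparison reported as supportive. Log time is an optional scale, but any gain from it would rest on an assumed distribution.

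In Method, require the first planned cervical exam to be recorded before the allocation is opened. Add the Bishop's score to the model only if it too is recorded before allocation, and state when it is collected.

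State separately how cesarean deliveries are handled in the primary outcome, and correct the sample-size statement on its own terms.

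The cost is two or three sentences in the statistics section, an ordering rule for an exam already planned and, if the Bishop's score is used, a stated time for it. No new procedures or patients are needed.

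### Do four-hourly cervical exams, with no dilation outcome listed, undermine the plan's stated interest in the labor curve?

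*Combined protocol and SAP*

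**What the plan says.** The Method section of the combined protocol and SAP introduces the exams with their purpose: "To determine the impact of the birthing balls on the labor curve". It then sets the timing: "patients will have a cervical exam within 15min of epidural placement", and afterwards "every four hours (or when clinically indicated) until complete cervical dilation". Ball use also ends at full dilation, so exams and intervention stop at the same milestone.

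Statistics and Analysis names the time from epidural catheter insertion to delivery as the primary outcome. On the rest it says: "Secondary outcomes include mode of delivery, maternal satisfaction and post-delivery complications". Dilation rate, time to full dilation and stage 1 length do not appear there, and no analysis of the serial exams is described. The same section gives the only usual-care distribution in the document: "historical FMC mean =/- SD from epidural insertion to delivery is 325+/-150min".

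The Background breaks the earlier peanut-ball study's 113-min reduction into "Stage 1 labor by 90min and Stage 2 labor by 23min".

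**The concern.** The exams are given a research purpose, and two parts of the plan seem not to serve it.

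- **Spacing.** A four-hour interval is long against a mean of 325 min. Most women would have the placement exam and at most one four-hourly exam after it, and two points do not trace a curve.
- **Analysis.** The outcome list has no measure to which the exams would contribute.

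A stage 1 or labor-curve result would be a natural thing to report, because the ball is used only in stage 1 and the Background credits stage 1 with 90 of the 113 min saved. If most of the information came from exams done at staff discretion, with the ball in view, a reader could not tell how much of an apparent difference reflected when women were checked. The wording also leaves open whether an indicated exam restarts the four-hour clock. At stake would be the credibility of a secondary claim about how the ball works.

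**Working it through.** **Inputs.** From Statistics and Analysis: time T from insertion to delivery has mean 325 and SD 150 min. From Method: exams every 240 min, ending at full dilation. The plan gives no figure for exams per woman, so there is none to reproduce. Its stated SD of 46% agrees with 150/325 = 46.2%. The sample size of 101 per group does not enter the count below, and nothing here vouches for it.

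**Step 1: delivery before each four-hourly exam.** Under a normal distribution:

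- P(T < 240) = Φ((240 − 325)/150) = Φ(−0.567) = 0.285
- P(T < 480) = Φ((480 − 325)/150) = Φ(1.033) = 0.849

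With the same mean and SD, gamma gives 0.320 and 0.854, and lognormal gives 0.319 and 0.866. If the clock starts at an exam 15 min after placement, the second four-hourly exam falls at 495 min. The normal figure is then Φ(170/150) = Φ(1.133) = 0.871.

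**Step 2: allow for exams stopping at full dilation.** In a vaginal birth with stage 2 of length S, a woman has at most one four-hourly exam after placement if T < 480 + S. The document gives no stage 2 length, so S is assumed:

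- S = 30: Φ((510 − 325)/150) = Φ(1.233) = 0.891
- S = 120: Φ((600 − 325)/150) = Φ(1.833) = 0.967

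Gamma gives 0.886 and 0.948. On these inputs the 85% is a lower bound.

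**Step 3: vary the mean.** The 325 min is historical data from the hospital, with neither parity nor technique stated. The trial enrols only nulliparous women, all given combined spinal-epidural analgesia. Take an assumed mean of 400 min, with SD 150 or 0.46 × 400 = 184:

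- P(T < 480) = Φ(80/150) = 0.703 or Φ(80/184) = 0.668; gamma gives 0.734 and 0.712
- With S = 60, at most one four-hourly exam: Φ(140/150) = 0.825 or Φ(140/184) = 0.777

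Most women would still have at most one four-hourly exam, but the exact 85% is not established for this population.

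**Step 4: is full dilation caught at a four-hourly exam?** This needs an exam at a multiple of 240 min between full dilation and delivery. The share of vaginal births with none depends on the assumed S and on how time to full dilation is modelled:

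| Assumed stage 2 (min) | No four-hourly exam in the interval |
|---|---|
| 30 | 86-89% |
| 60 | 71-77% |
| 90 | 55-67% |
| 120 | 39-57% |

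The answer moves from nearly all to about half or fewer on an input that the document does not supply.

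**Step 5: the clock.** If an indicated exam restarts the clock, the share of women still in stage 1 who are examined between 210 and 270 min is 65%, 53%, 59% and 72% for assumed mean waits of 60, 120, 240 and 480 min (the shorter of an exponential wait and 240 min). With a fixed clock it is all of them. The waits are assumptions too.

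**Step 6: set the exams against the outcomes.**

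| Outcome in the plan | Uses cervical dilation? |
|---|---|
| Insertion to delivery (primary) | No |
| Mode of delivery | No |
| Maternal satisfaction | No |
| Post-delivery complications | No |

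No listed estimate or test changes, whatever the exams record.

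**Step 7: would a tighter measure help?** Full dilation by 240 min, with 101 per arm and a two-sided 5% test, has power of about 44-68% for a 42-min reduction (0.13 × 325 = 42.25) placed wholly in stage 1, with S from 30 to 90 min. Exact times would give 66-86%. Prespecifying that measure would spend power on a result that the plan does not promise.

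**The case for a change.** The best argument for a change is that the plan states an objective and nowhere gives its endpoint or method. The word include in the secondary-outcome sentence leaves the list open but does not supply an analysis. Any definition of a curve or a stage 1 duration could then be chosen after the data are seen. The Implications section foresees changes to local practice and to public health policy, and the remedy is cheap: delete the clause, or label the curve exploratory and record the time of each exam.

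The mismatch between the two sections is real, and so is the thinness of the four-hourly exams taken alone. The step to harm is weaker:

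- Indicated exams are part of the same schedule. Their number is unknown, so a count of four-hourly exams cannot show that the full data are too sparse.
- Nothing in the document suggests more checking in one arm, and equal checking creates no expected false difference.
- The harm depends on a result that the plan never commits to report.
- The fuller remedy (interval censoring, cesarean before full dilation as a competing event, rules for the clock) writes down choices that an analyst would make if a curve were reported. It corrects no stated method.

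**Conclusion.** The concern does not call for a change. The Method section names a labor-curve purpose that Statistics and Analysis does not take up. If the historical 325 ± 150 min applies to this population, about 85% or more of usual-care women would have at most one four-hourly exam after placement. At an assumed mean of 400 min, 67-73% (normal or gamma) would deliver before the second one. Either way, a curve would lean on indicated exams whose number is not given.

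The effect on the primary outcome and the listed secondary outcomes is nil, because none of them uses dilation. The figures for full dilation going unrecorded at a four-hourly exam (39-89%) and for the restarting clock (53-72%) rest on assumed stage 2 lengths and exam waits, so they cannot carry the point. This is missing detail about a descriptive use of the exams. An analyst who reports a curve can describe it as exploratory and treat full dilation as known only to lie between two exams. Editing the clause would tidy the text and gain nothing in the trial's conclusions.
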